6. SELECTION AND WITHDRAWAL OF SUBJECTS

6.1. Subject Inclusion Criteria

No subject should be assigned to treatment until all eligibility criteria have been satisfied. To qualify for the study a subject must:

1. Be a male or female and be ≥ 18 years of age
2. If a female of childbearing potential, have a negative urine pregnancy test and be using an effective contraception method (ie, abstinence, intrauterine device [IUD], hormonal [estrogen/progestin] contraceptives, or barrier control) for at least one menstrual cycle prior to study enrollment and for one menstrual cycle following end of study, or be surgically sterile
3. Have symptoms of unilateral idiopathic adhesive capsulitis for at least 3 months but not more than 12 months before the screening visit and be in Stage 2 (frozen or adhesive stage), as determined by the investigator
4. Have normal range of motion in the contralateral shoulder, as determined by the investigator
5. Have restricted active range of motion (AROM) in the affected shoulder defined as: a deficit of at least 60° in total AROM in the affected shoulder as compared with the total AROM in the contralateral shoulder and a deficit of at least 30° in AROM in at least one of the following planes as compared with the contralateral shoulder:
 - Forward flexion
 - Abduction
 - External rotation
 - Internal rotation
6. Voluntarily sign and date an informed consent agreement approved by the Institutional Review Board/Independent Ethics Committee (IRB/IEC). The subject must also sign an authorization form to allow disclosure of his protected health information (PHI). The PHI authorization form and informed consent form may be an integrated form or may be separate forms depending on the institution.

6.2. Subject Exclusion Criteria

A subject will be excluded from study participation if he/she:

1. Is a pregnant female or female intending to become pregnant during the study or a female breastfeeding a child
2. Has received treatment for adhesive capsulitis or is planning to receive treatment for adhesive capsulitis at any time during the study including but not limited to:
 - physical therapy or acupuncture within 2 weeks before the first injection of study drug
 - intra-articular or intrabursal injection(s) of lidocaine; suprascapular nerve blocks; corticosteroids, electroanalgesic and/or thermoanalgesic modalities within 1 month before the screening visit
 - intra-articular or intrabursal injection(s) of sodium hyaluronate and/or glenohumeral distension arthrography within 3 months before the screening visit
 - surgical intervention (including shoulder manipulation under anesthesia) at any time
3. Has any of the following conditions, as determined by the investigator to be potentially confounding to the evaluation of safety and efficacy:
 - Adhesive capsulitis as a result of traumatic injury (ie, direct injury to the shoulder such as fracture of the humerus or clavicle immediately preceding the onset of this episode of adhesive capsulitis). Traumatic events in the past that are not temporally related to the onset of this episode of adhesive capsulitis would not necessarily exclude a subject from participating in the study.
 - Active subacromial impingement in the affected shoulder
 - Calcified tendonitis in the affected shoulder
 - Glenohumeral joint arthritis in the affected shoulder
 - Arthrosis of the affected shoulder
 - Chondrolysis of the affected shoulder
 - Subscapularis tendon rupture of the affected shoulder
 - Other rotator cuff injuries of the affected shoulder
 - Uncontrolled hypertension
 - Uncontrolled diabetes
 - Uncontrolled thyroid disease
 - History of thrombosis or post-thrombosis syndrome
 - Physical impairment that would preclude performing the protocol defined exercises
 - Active infection in area to be treated
 - Clinically significant neurological disease
 - Bleeding disorder

- Chronic use of anticoagulation medications and the subject cannot be cleared medically to stop taking medication for 7 days prior to each injection. Less than or equal to 150 mg aspirin is allowed during the study.
 - Known active hepatitis A, B, or C
 - Other significant medical condition (eg, morbid obesity, cervical disc disease), which in the investigator's opinion would make the subject unsuitable for enrollment in the study
4. Is unwilling or unable to cooperate with the requirements of the study including completion of all scheduled study visits.
 5. Has received oral or intravenous steroids for any reason within 3 weeks before the screening visit
 6. Has received an investigational drug or treatment within 30 days before the first dose of study drug.
 7. Has a known allergy to collagenase or any other excipient of AA4500 or any other procedural medication.
 8. Has, at any time, received collagenase for the treatment of adhesive capsulitis.
 9. Is unable to undergo an x-ray or MRI (contraindication) evaluation of the affected shoulder.
 10. Is planning to be treated with commercial XIAFLEX at any time during the study

6.3. Subject Withdrawal Criteria

Each subject has the right to withdraw from the study at any time without prejudice. If a subject withdraws from the study, the reason(s) must be stated in the subject's medical record and recorded onto the case report form (CRF). A final evaluation of the subject should be performed before discharge.

The investigator may discontinue any subject's participation if he or she feels it is necessary for any reason, including any adverse event, clinically significant adverse change in any laboratory test, or failure to comply with the protocol including the use of anticoagulants or inability to comply with the visit schedule.

Subjects who withdraw from the study or who are discontinued for any reason should have a final evaluation performed either before withdrawal or as soon as possible after discontinuation. Please refer to Day 95/Early Withdrawal on Schedule of Assessments for details (Table 1).

Subjects who withdraw from the study will not be replaced unless it is mutually agreed upon in writing by the respective principal investigator and Auxilium Pharmaceuticals, Inc.'s medical monitor.

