5. INVESTIGATIONAL PLAN

5.1. Overall Study Design and Plan: Description

This study is a Phase 2b, double-blind, placebo-controlled study of the safety and efficacy of AA4500 for the treatment of adhesive capsulitis of the shoulder. To be eligible for treatment, a subject must have unilateral idiopathic adhesive capsulitis of the shoulder with restricted range of motion in the affected shoulder for at least 3 months but not more than 12 months. Subjects will be screened for study eligibility within 28 days before injection of study drug.

Approximately 300 adult women and men are to be enrolled in this study. Following screening and determination of study eligibility, eligible subjects will be randomized 3:1 to receive AA4500 0.58 mg/1 mL or placebo. Subjects will receive up to 3 injections of study drug. Each injection will be separated by a minimum of 21 days. Subjects will also be instructed in home shoulder exercises after the first injection.

Table 1: Study AUX-CC-871 Assessments

Procedures	Screening Day -28 to -1	Injection 1 (Day 1)		Day 8 (± 2 days)	Injection 2 (Day 22) and Injection 3 (Day 43)		Day 29 and Day 50 (±2 days)	Follow-up Day 64 (+7 days)	EOS: Day 95 (± 7 days)/ Early Withdrawal
		Prc- injection	Post- Injection		Prc- injection	Post- Injection			
Obtain informed consent	X								
Medical history/AC history	X								
Prior/concomitant medications/procedures	X	X	X	X	X	X	X	X	X
PE with body weight, height, hand dominance	X								
Vital signs	X	X ^a	X ^a	X	X ^a	X ^a	X	X	X
Targeted examination of the affected shoulder:									
• Inspection, signs of instability and impingement	X ^b								
• AROM and PROM	X ^b	X		X	X	X	X	X	X
• ASES Pain sub-scale	X								
• ASES Function sub-scale	X								
• Pain with movement	X								
12-lead ECG	X								
X-ray of the affected shoulder	X								
MRI of affected shoulder	X								
Clinical laboratories	X								X
Urine pregnancy testing (dipstick)	X	X			X				
Anti-AUX-I/anti-AUX-II antibodies and Nabs	X								X
Randomization		X							
Compliance with home shoulder exercises				X	X	X	X	X	X
Investigator assessment of improvement with treatment									
Subject satisfaction with treatment									
Injection site reactions/local tolerability		X	X	X	X	X	X	X	X
Adverse events	X	X	X	X	X	X	X	X	X
Instructions for home shoulder exercises									
Eligible for retreatment (yes/no)					X ^c				

AROM=active range of motion; PROM=passive range of motion; VAS=visual analogue scale

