7.11. Treatment

Subjects may receive up to a maximum of 3 injections of study drug. Each injection will be separated by a minimum of 21 days.

Subjects will receive Injection 1 on Day 1 of the study. Administration of subsequent injections (ie, Injection 2, Injection 3) will be determined by the guidelines outlined in Table 2:

- Do not retreat: Subjects who meet all criteria for ‘do not retreat’ after Injection 1 or Injection 2 will not receive subsequent injection(s).
- Retreat: Subjects who meet all the criteria for ‘retreat’ after Injection 1 or Injection 2 will be eligible to receive subsequent injection(s) provided there are no safety issues (eg, adverse events; allergic reaction), as determined by the investigator.
- Investigator-Discretion: Subjects who do not meet the criteria for ‘do not retreat’ or ‘retreat’ after Injection 1 or Injection 2, will receive additional treatment at the discretion of investigator.

Table 2: Guidelines for Retreatment of Affected Shoulder

	Do Not Retreat^a	Retreat^b
Forward flexion:		
Active (sitting)	≥160°	<140°
Passive (supine)	≥160°	<140°
Abduction:		
Active (sitting)	≥160°	<140°
Passive (supine)	≥160°	<140°
External rotation with the elbow up to 90° abduction:		
Active (sitting)	≥45°	<30°
Passive (supine)	≥45°	<30°
Internal rotation with the elbow up to 90° abduction:		
Active (sitting)	≥45°	<30°
Passive (supine)	≥45°	<30°
^a Do not retreat if all measurements criteria are met. ^b Retreat if all measurement criteria are met and if the investigator determines there are no safety issues (eg, ongoing adverse events).		
IF NEITHER THE CRITERIA FOR 'DO NOT RETREAT' OR 'RETREAT' ARE MET AFTER INJECTION 1 OR INJECTION 2, THEN ADDITIONAL TREATMENT WILL BE AT THE DISCRETION OF INVESTIGATOR.		

7.11.1. Subjects Not Eligible for Injection 2 and/or Injection 3

Subjects who are not eligible for Injection 2 and/or Injection 3 (eg, successfully treated or ongoing adverse events) will have follow-up visits on Day 43 (Section 7.13.5) and Day 64 (Section 7.13.7). Subjects who are not eligible for Injection 2 and/or Injection 3 will not be required to have a study visit on Day 29 and/or Day 50, respectively. Subjects who are not eligible for Injection 2 because of ongoing adverse events may receive Injection 3 at the discretion of the investigator.

All subjects will have a final follow-up visit on Day 95.

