10.1.2. Efficacy

For ROM, baseline is before injection on Day 1. Baseline for all other efficacy parameters is the screening visit.

The primary endpoint is the change (degrees) from baseline to the Day 95 follow-up in active forward flexion in the affected shoulder.

Secondary endpoints are:

1. Change from baseline to Day 95 in ASES function sub-scale
2. Change (degrees) from baseline to the Day 95 follow-up in abduction
3. Change from baseline to the Day 95 follow-up in pain with movement using a 11-point VAS
4. Change (degrees) from baseline to the Day 95 follow-up in internal rotation
5. Change from baseline to the Day 95 follow-up in external rotation
6. Change from baseline to the Day 95 follow-up in ASES pain sub-scale
7. Investigator satisfaction with treatment at the Day 95 follow-up
8. Subject satisfaction with treatment at the Day 95 follow-up

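### Section 6.3 lets an adverse event or non-compliance end study participation with only an exit evaluation, while 7.11.1 keeps overlapping subjects to Day 95, so primary-endpoint readings can be lost avoidably

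*Protocol*

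**What the plan says.** Two parts of the protocol cover overlapping situations.

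- **Section 6.3, Subject Withdrawal Criteria.** The investigator may end any subject's "participation if he or she feels it is necessary for any reason, including any adverse event"; a clinically significant laboratory change and failure to comply with the protocol are also named. Subjects who leave for any reason "should have a final evaluation performed either before withdrawal or as soon as possible after discontinuation". For its content, 6.3 refers to the Table 1 column headed "Day 95 (± 7 days)/ Early Withdrawal". Section 6.3 does not distinguish stopping injections from leaving the study, and it asks for no later Day 95 visit.
- **Section 7.11.1, Subjects Not Eligible for Injection 2 and/or Injection 3.** Subjects who do not get a further injection ("eg, successfully treated or ongoing adverse events) will have follow-up visits on Day 43") remain in the study and are also seen on Day 64. It closes: "All subjects will have a final follow-up visit on Day 95". The note under Table 1 repeats that sentence. Neither place makes an exception for subjects discontinued under 6.3.

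The primary endpoint (Section 10.1.2) exists only at Day 95: "The primary endpoint is the change (degrees) from baseline to the Day 95 follow-up in active forward flexion in the affected shoulder".

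**The concern.** An ongoing adverse event is a reason to withhold an injection under 7.11.1, with follow-up to Day 95. It is also a reason to end participation under 6.3, with one exit evaluation. Nothing tells a site which applies. If 6.3 is applied, the subject has no Day 95 reading, and no analysis plan can recover a visit that was never held.

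The shared column adds a second weakness. An evaluation made weeks early is filed under the same heading as Day 95. Shoulder motion tends to improve over the study, so an early reading that passes for Day 95 would understate the gain.

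Adverse events are also unequal between arms. The appended record gives non-serious events (5% reporting threshold) in 188/237 (79.3%) on AA4500 and 37/84 (44.0%) on placebo. A rule that adverse events can trigger could therefore act unequally. The 20% dropout allowance in Section 10.3 protects power, not against bias from unequal loss.

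**Working it through.** **1. The plan's own figure.** Section 10.3: difference 15 degrees, SD 30, 240 subjects at 3:1 (180/60). Two-sided 5% is assumed, since the side is not stated.

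- SE = 30 × √(1/180 + 1/60) = 4.47
- Power = Φ(15/4.47 − 1.96) = 91.8%
- 240/0.8 = 300 (225/75)

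The stated power of at least 90% and the 300 both reproduce. With all 300 observed, SE = 30 × √(1/225 + 1/75) = 4.0 and power = Φ(3.75 − 1.96) = 96.3%.

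**2. Were exit readings labelled Day 95?** Sections 7.13.8, 7.14.11 and 7.14.12 place the two global ratings only at Day 95. Counts from the appended results record:

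| | AA4500 | Placebo |
|---|---|---|
| Started | 237 | 85 |
| Completed | 219 | 80 |
| Subject satisfaction at Day 95 | 229 | 81 |
| Investigator assessment at Day 95 | 229 | 82 |
| Active forward flexion, Day 95 change | 217 | 79 |

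At least 229 − 219 = 10 AA4500 non-completers and 1 to 2 placebo non-completers have a rating labelled Day 95. Exit evaluations are the likeliest source, but this is inference. For forward flexion the counts lie below the completers, which points to loss rather than replacement.

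**3. Who left, and why.** Non-completion was 18/237 (7.6%) and 5/85 (5.9%), Fisher p = 0.81. Adverse event: 1 and 1 (0.4% and 1.2%). Protocol violation: 2 and 0. Together these are 3/237 (1.3%) and 1/85 (1.2%). Subject withdrawal or loss to follow-up accounts for 15 of 18 and 3 of 5.

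**4. If exit readings of forward flexion stood in for Day 95.** No passage states this; it is an assumption. Further assumptions: linear recovery, true difference 15 degrees, exit at day t = 29 or 50, and placebo gain G0 = 12 (exercise-only cohort of AUX-CC-870, Section 3.5.2) or 35.9 (placebo arm, appended record). With exit proportions pA and pP:

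Estimate = 15 − (1 − t/95) × [pA(G0 + 15) − pP·G0]

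Power = Φ(estimate/4.0 − 1.96)

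The worst corner is G0 = 35.9, t = 29, with 1 − 29/95 = 0.695. At 3/237 and 1/85:

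15 − 0.695 × [0.01266 × 50.9 − 0.01176 × 35.9] = 15 − 0.695 × 0.222 = 14.85

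| Exits AA4500 / placebo | Estimate (degrees) | Power |
|---|---|---|
| 3/237, 1/85 (realised, adverse event or protocol violation) | 14.85 to 14.90 | 96% |
| 18/237, 5/85 (all non-completers) | 13.8 to 14.4 | 93% to 95% |
| 10% / 5% (assumed) | 12.7 to 14.0 | 89% to 94% |
| 20% / 10% (assumed) | 10.4 to 13.0 | 74% to 90% |

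Part of each reduction is plain dilution, not arm imbalance. Equal exits of 15% in both arms already give 15 − 0.695 × 0.15 × 15 = 13.4 at t = 29 and 13.9 at t = 50. That is about a third to a half of the 20%/10% loss.

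**5. If the readings are simply lost.** With 217/79 analysed, SE = 30 × √(1/217 + 1/79) = 3.94 and power = Φ(15/3.94 − 1.96) = 96.7%. Precision was not hurt. Any bias from who is missing cannot be computed from the document.

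**The case against.** The strongest reply is about scope. Section 7.11.1 is written for subjects still in the study who miss an injection, and it already separates missing an injection from leaving. Section 6.3 covers leaving, and Table 1 foresees early withdrawal. On that reading, the sentence about a Day 95 visit means everyone still participating. Moreover, 6.3 gives a permission, not an instruction.

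This stands in part. A reader might infer a flat contradiction, and the text does not support that: it is an overlap that was never reconciled. But the overlap is real, because an ongoing adverse event falls under both sections and neither refers to the other.

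A reader might also infer that exit readings are analysed as Day 95. No passage says so. A shared column lists procedures, Day 95 has its own ± 7 day window, and visit assignment commonly belongs to the SAP, which is not at hand. The rating counts show that labels can blur, but the forward flexion counts do not show replacement of the primary endpoint.

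Finally, a reader might infer arm-related bias from the adverse-event imbalance. Those events are largely bruising, contusion and local pain, and exits for adverse events were 1/237 and 1/85. The record does not show it.

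It is also fair to say that most non-completers left by their own decision or were lost, which no change to 6.3 would alter.

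**Conclusion.** The point holds as an avoidable weakness in what the protocol fixes. Sections 6.3 and 7.11.1 allow opposite follow-up for the same event, so a Day 95 primary reading can be lost when the subject could have been kept, and an exit evaluation can carry a Day 95 label.

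The realised size was small. Four subjects left for an adverse event or protocol violation. Even if their exit readings had replaced Day 95, the pessimistic model moves 15 degrees only to about 14.85, with power still 96%. The larger reductions, down to 10.4 degrees and 74% power, need assumed exit rates of 20% and 10%, linear recovery, and use of exit readings as Day 95. They describe what the wording could permit, not what happened. Arm-related bias remains a possible risk, not a demonstrated one. The sample size is unaffected. This is a cheap improvement that should be made.

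**What to change.** Reconcile 6.3 with 7.11.1 and the Table 1 note:

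- State in 6.3 that a subject whose study injections end is still asked to attend the remaining visits, or at least Day 95, unless the subject withdraws consent or cannot attend. The last exception is needed because 6.3 itself names inability to keep the visit schedule.
- Record the date and reason for ending injections separately from those for leaving the study. Section 6.3 already asks for the reason when a subject withdraws; the separate record for injections is the addition.
- Give early withdrawal its own visit label in Table 1 and the CRF, counted as Day 95 only when it falls within Day 95 ± 7 days.

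The clinical grounds listed in 6.3 are not changed. The cost is wording in 6.3 and Table 1, one or two CRF fields, and a few more follow-up visits of the kind 7.11.1 already foresees.

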7. PROCEDURES AND TREATMENTS

7.1. Randomization

Following screening and determination of study eligibility, subjects will be randomized 3:1 to receive AA4500 0.58 mg or placebo. A central randomization scheme will be used with an interactive web response system (IWRS).

7.2. Blinding

This will be a double-blind study in which the investigator, study subject, and other study personnel involved in the evaluation of the subject efficacy or safety are blinded to study drug treatment. All precautions will be taken to ensure that the blinding of AA4500 and placebo is maintained throughout the study period. Unblinding will not be permitted by the study site unless it is deemed necessary for appropriate treatment of a medical emergency. The study site will have the ability to immediately determine treatment identification in the event of an emergency by swiping the label portion of the drug kit with an alcohol pad; however, the medical monitor at Auxilium must be notified immediately.

7.3. Reconstitution of Study Drug

Before reconstitution, designated study personnel will visually inspect the study drug vials to determine the integrity and acceptability of the lyophilized drug product and sterile diluent(s) for reconstitution. The vial containing lyophilized drug product is to be reconstituted with 1.55 mL sterile diluent. The written procedures for inspection of the study drug vials and reconstitution of study drug will be provided in the Pharmacy Manual.

Designated study personnel will maintain a record of the date and time of reconstitution and dispensation of the assigned treatment. The reconstituted A4500 solution can be kept at room temperature (20° to 25°C/68° to 77°F) for up to one hour or refrigerated at 2° to 8°C (36° to 46°F) for up to 4 hours prior to administration.

[figure not shown]
7.4. Location of Injection Site

The subject will be supine on the examination table and the affected arm should be passively externally rotated to the subject's level of pain tolerance with the elbow at the side (against the body) and flexed to 90°. **If the affected arm cannot be passively externally rotated to at least the neutral position, the injection cannot be administered.** Pendulous breasts may be retracted.

The bicipital groove and the tip of the coracoid process will serve as the injection site landmarks. These landmarks should be identified by inspection and palpation. Each landmark is marked with a surgical marker. Internal and external rotation of the shoulder can aid in identifying the approximate location of the bicipital groove. In subjects with pendulous breasts, the breasts may be retracted medially to aid in identifying the injection site.

The injection site, which is located in the coronal plane midway between the bicipital groove and the tip of the coracoid process, will be marked with a surgical marker as shown in Figure 1. The middle marking will serve as the location of the injection site.

Figure 1: Injection Site

[name] and [name]

7.5. Administration of Local Anesthesia

The affected arm should be passively externally rotated to the subject's level of pain tolerance with the elbow at the side (against the body) and flexed to 90°. **If the affected arm cannot be passively externally rotated to at least the neutral position, the injection cannot be administered.** Pendulous breasts may be retracted.

1. After the injection site is identified as described in Section 7.4, the area should be prepped with antiseptic antimicrobial skin prep such as ChloroPrep® (chlorhexidine) or Betadine®.
2. The local anesthetic should be administered at the previously marked injection site. Using the 20-gauge, 1 ½ inch needle and 10 cc control syringe, administer up to 10 ccs of local anesthetic. The injection of local anesthetic will create the skin puncture site and path for the 22-gauge Sprotte® spinal needle to follow. The Sprotte® spinal needle will be used to inject study drug.

The local anesthetic should be administered as follows:

3. First, numb the skin at the injection site by injecting approximately 1/3 of the local anesthetic. Then, inject the remaining local anesthetic, as necessary, along the needle path extending directly towards the anterior shoulder capsule. Be sure to withdraw on the plunger of the syringe prior to injection of the local anesthetic to ensure that you are not injecting intravascularly. This injection should be perpendicular to the subject's skin at the injection site. Do not penetrate the shoulder capsule with the needle.
4. Be sure to allow a minimum of 10 minutes to elapse between the injection of the local anesthetic and the administration of study drug. Do not allow more than 30 minutes to elapse, as the anesthetic effect may wane.

